4.2 Primary Endpoint

The primary endpoint will be the proportion of subjects who achieve wound closure by or at 12-weeks post treatment with MIRODERM.

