6.7 Follow-up Visits (Visits 3-14; Weeks 4-15)

6.7.1 Wound Closure Assessment

Wound will be assessed for closure. If wound is closed subjects will receive no further treatment, have their wound size documented (per 6.8.2), and will be asked to return in 1-week for a confirmation visit.

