6.7.2 Wound assessment and size documentation

Wound will be assessed for gross dimensions and infection. If an infection is an AE form should be completed and ***the subject will be discontinued from the study.***

The area of the wound will be documented using the E-Z Graph Wound Assessment System and photography.

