6.9 Study Exit

Subjects will be discontinued from the study per protocol. Under the following circumstances:

- Subject's index wound has been determined to be fully closed and remains closed at their 1-week follow-up confirmation
- Subject had completed their 12-week post-treatment follow-up and their index wound has not completely healed
- Subject presents with osteomyelitis of the study DFU or an infection of the study DFU
- Subject voluntarily withdraws consent.
- Subject lost-to-follow-up
- Subject death

When a subject is study exited, patients are no longer considered participants in the study and have no further obligations under the protocol. patients may undergo continued care as deemed appropriate by physician of record.

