6.10.4 Wound Assessment and Treatment CRF

This will document whether the wound is closed. To be closed there must be 100% epithelialization of the wound, no discernable exudate, and no further need for dressing.

Wound area and volume will be assessed by gross measurement of length, width and depth and assessed for infection.

With initial application during the treatment visit, and then when clinically indicated additional applications of MIROMESH will be documented including lot number, type, and size of MIRODERM Biologic Wound Matrix.

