6.10.6 Study Discontinuation CRF

This form will document when and the conditions under which a subject is exited from the study.

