7 STATISTICAL CONSIDERATIONS

As a prospective clinical outcome and survivorship study, there are no specific hypotheses to be tested. Data analysis may be conducted intermittently as needed or as requested by investigators without a power penalty and consist primarily of summary statistics and inferential statistics for changes in dependent measures over time.

Specific data analyses may include but are not limited to:

- **Demographics** and other pre-treatment characteristics will be summarized and characterized with appropriate descriptive statistics including error measures. Statistics may include mean, mode, median, range, inter-quartile range, minimum, maximum, frequency, cumulative frequency percentage and cumulative percentage. Results may be presented in a narrative and graphically.
- **Subject reported and dependent outcome measures** will be summarized and thoroughly characterized with the appropriate descriptive statistics including error measures. Statistics may include mean, mode, median, range, inter-quartile range, minimum, maximum, frequency, cumulative frequency percentage and cumulative percentage. Results may be presented in a narrative and graphically. Measures collected at multiple timepoints will also be analyzed using inferential statistics to assess changes over time, of special interest post-treatment changes from pre-treatment values. As appropriate a repeated measure ANOVA or Wilcoxon signed rank

test will be completed for each outcome measure. If a significant trend is identified, significance among time points may be further explored using the appropriate pair-wise comparisons. In all cases a p-value equal to or less than 0.05 will be considered significant. No corrections for multiple pair-wise comparisons will be made.

Missing data will be ignored in statistical calculations while using the appropriate n (sample size) for any given statistic or test.

Sample Size Justification: The precision of the estimate of the proportion of subjects who successfully close will be determined.

Assumptions:

- A minimum 50 subjects
- A 95% Confidence Interval of the estimate
- A 2-sided confidence interval
- Using exact Clopper-Pearson estimation

The Confidence Intervals (CI) at selected success rates are as follows:

- @ 25%; CI = 25.4% Boundaries 13.8%-39.3%
- @ 50%; CI = 28.9% Boundaries 35.5%-64.5%
- @ 75%; CI = 25.4% Boundaries 60.7%-86.2%

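### Section 7 ignores missing data without exempting the primary endpoint, and the plan never says whether a treated subject who exits early with an open wound stays in the closure-rate denominator

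*Combined protocol and SAP*

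**What the plan says.** Section 4.2 defines the single primary endpoint: "The primary endpoint will be the proportion of subjects who achieve wound closure by or at 12-weeks post treatment with MIRODERM". The synopsis gives the same endpoint in similar words. Neither names an analysis set. Under Sections 6.5.1.1 and 6.6.4 a person is an active subject from consent but is enrolled only once treated with MIRODERM. Neither status is tied to the primary proportion.

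Closure is checked at every weekly follow-up visit. Section 6.7.1 reads: "Wound will be assessed for closure. If wound is closed subjects will receive no further treatment". The result goes on the wound CRF, of which Section 6.10.4 says: "This will document whether the wound is closed". Infection is assessed next, under Section 6.7.2, and if it is present "the subject will be discontinued from the study". Section 6.9 lists the same exit: "Subject presents with osteomyelitis of the study DFU or an infection of the study DFU". It also lists withdrawal, loss to follow-up and death, and adds: "When a subject is study exited, patients are no longer considered participants in the study and have no further obligations under the protocol". The reason for leaving is recorded; Section 6.10.6 says: "This form will document when and the conditions under which a subject is exited from the study".

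The only statement on missing outcomes is in Section 7: "Missing data will be ignored in statistical calculations while using the appropriate n (sample size) for any given statistic or test".

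**The concern.** Infection and osteomyelitis are foreseen in this population: Section 5.1 lists them as treatment risks and Section 14.2 as reportable events. Once such a subject exits, no Week 12 status is collected. If that status is then treated as missing, Section 7 allows the subject to leave n, and the subjects removed are ones whose ulcer did badly.

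The closure proportion is the only primary result of a single-arm study, so no control arm shares the distortion. The synopsis and Section 7 intend it for comparison with historical controls, the literature and a history of non-healing. Two analysts could report different primary rates from the same data, both consistent with the plan. Section 7 also allows analyses at intervals as needed, so a denominator left open could be settled after results have been seen.

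**Working it through.** **1. The plan's own figures.** Section 7 gives two-sided 95% exact Clopper-Pearson intervals for n = 50. With lower limit Beta(0.025; x, n-x+1) and upper limit Beta(0.975; x+1, n-x):

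- 25% (x = 12.5): 13.84 to 39.26, width 25.42; stated 13.8-39.3, 25.4
- 50% (x = 25): 35.53 to 64.47, width 28.95; stated 35.5-64.5, 28.9
- 75% (x = 37.5): 60.74 to 86.16, width 25.42; stated 60.7-86.2, 25.4

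These reproduce. They are correct for a fixed n of 50 and make no allowance for exits.

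**2. The two readings.**

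- (a) The open wound recorded at exit is an observed non-closure, and n is all treated subjects. Rate = x/n.
- (b) The Week 12 outcome is missing and the subject leaves n. Rate = x/(n-k), where k is the number of exits dropped.

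The ratio of (b) to (a) is n/(n-k). It exceeds 1 whenever k > 0, so (b) is above (a) whenever there is at least one closure. The endpoint is met as soon as closure is recorded, so a subject with a standing closure has an outcome whenever follow-up stops. Leaving reopened wounds aside, the subjects who can be dropped are those not closed.

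**3. Infection and osteomyelitis exits only.** The documents give no exit rate, so k is an assumption; so are the closure counts. With 50 treated:

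| Closures x | (a) x/50 | (b) k = 2, x/48 | (b) k = 4, x/46 | (b) k = 6, x/44 |
|---|---|---|---|---|
| 15 | 30.0% | 31.3% (+1.3) | 32.6% (+2.6) | 34.1% (+4.1) |
| 20 | 40.0% | 41.7% (+1.7) | 43.5% (+3.5) | 45.5% (+5.5) |
| 25 | 50.0% | 52.1% (+2.1) | 54.3% (+4.3) | 56.8% (+6.8) |

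At 25 closures and k = 4 the 95% interval is 39.0-69.1 under (b) and 35.5-64.5 under (a). Enrolling the maximum of 65 does not remove the difference: with 4 dropped, 26/61 = 42.6% against 26/65 = 40.0%, or +2.6 points.

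**4. All exits.** Assume 4 infection or osteomyelitis exits and 4 withdrawals or losses, with 50 treated:

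| Closures x | All 8 not closed, x/50 | All 8 dropped, x/42 | The 4 withdrawals or losses closed, (x+4)/50 |
|---|---|---|---|
| 15 | 30.0% | 35.7% (+5.7) | 38.0% |
| 20 | 40.0% | 47.6% (+7.6) | 48.0% |
| 25 | 50.0% | 59.5% (+9.5) | 58.0% |

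At 15 and 20 closures the last column is above the dropped-case rate; at 25 it is below. So whether dropping overstates what full follow-up would have shown depends on outcomes nobody observed.

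**The case against.** The best defence is that reading (a) is already what the plan implies. Enrolled means treated. The synopsis sets a minimum of 50 enrolled, and the precision calculation uses the same 50 with no attrition allowance. Closure is assessed at every visit, before infection. An infected open wound is therefore an observed state, not obviously a missing value. The missing-data sentence follows the text on repeated measures and pair-wise tests, where a varying n is natural. All this stands, and it makes (a) the more natural reading. It does not exclude (b): the sentence covers any statistic, and no section carves out the primary endpoint. Section 6.2 groups infection exits with subjects who do not complete per protocol, while Section 6.9 lists them under discontinuation per protocol. Those two descriptions need reconciling. A subject lost to follow-up may have no assessment at the time of leaving at all.

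A second defence is size. There is no margin or success threshold for the closure rate, and 2 to 4 infection exits move it by 1.3 to 4.3 points against a planned interval 28.9 points wide at 50%. The comparison is fair, but the interval measures sampling error and does not cover selective removal of non-closures. Recorded exit reasons would allow recalculation, yet no section requires exits to be reported by cause.

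Two stronger readings are tempting. A reader might infer that the plan instructs the analyst to drop infection exits; it only permits this. A reader might also infer that dropping exits always overstates the true rate. That is certain only against reading (a). In the 25-closure example, if the 4 withdrawals or losses and one infection exit would all have closed by Week 12, the rate is 30/50 = 60.0%, above 25/42 = 59.5%.

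**Conclusion.** The point holds as an unresolved denominator combined with a stated rule that permits the less favourable choice. Nothing in the precision figures is wrong. Relative to counting infection and osteomyelitis exits as not closed, dropping 2 to 6 of them from 50 raises the closure rate by 1.3 to 6.8 points at 15 to 25 closures. Exit and closure counts are assumptions; the multiplier n/(n-k) is exact.

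The upward direction rests on treating an infection or osteomyelitis exit as a non-closure. That is plausible, because the wound was open at exit, but the Week 12 status is not observed. For withdrawals and losses to follow-up the direction is not determined. Because this rate is the sole primary result and is meant for external comparison, the rule should be fixed before the data are analysed.

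**What to change.** Add to Section 7:

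> The primary denominator is every subject who received at least one MIRODERM application. A subject counts as closed only if the wound was assessed closed at or before 12 weeks and was not found reopened at the last available assessment, unless it was again assessed closed at or before 12 weeks. A subject who exits for any reason with an open or reopened wound, or with no closure assessment, counts as not closed. The general rule on ignoring missing data does not apply to the primary endpoint.

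The clause on reopening is needed because Sections 6.1 and 6.8.1 return a reopened wound to follow-up. Without it, a wound once assessed closed that reopened and then exited infected could score as a closure. Subjects found closed or infected at the Treatment Visit before any application (Sections 6.6.1 and 6.6.3) stay outside n.

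Also state that a subject closed by 12 weeks but lost before the confirmation visit counts as closed in the primary analysis and as not closed in a sensitivity analysis. Report exits by cause. Give the observed-case proportion, and a bound that counts withdrawals and losses to follow-up as closed.

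The cost is a short protocol amendment, since protocol and SAP are one document. No new data, visits or forms are needed, and the clinical exit rules are unchanged. The reported rate may be somewhat lower, and it is conservative for withdrawals and losses: in the 25-closure example with 4 such exits, 50.0% could be up to 8 points too low (29/50 = 58.0%). The bound shows this. Handling of exits in the Kaplan-Meier curve could be specified at the same time, but that is optional.

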
Schedule of Visits
	
 1 Assessment and Roll-in (2-weeks prior to procedure) 2 Index Procedure 3 1-Week post-procedure (\pm 2 days) 4 2-Week post-procedure (\pm 2 days) 5 3-Week post-procedure (\pm 2 days) 6 4-Week post-procedure (\pm 2 days) 7 5-Week post-procedure (\pm 2 days) 8 6-Week post-procedure (\pm 2 days) 9 7-Week post-procedure (\pm 2 days) 10 8-Week post-procedure (\pm 2 days) 11 9-Week post-procedure (\pm 2 days) 12 10-Week post-procedure (\pm 2 days) 13 11-Week post-procedure (\pm 2 days)

	
14 12-Week post-procedure (\pm 2 days)
 
15 Confirmation: 13-Week post-procedure (\pm 2 days)
 
All subjects will be offered a \$25 gift card for completing weekly follow-up during the treatment phase.

Study Duration	1 Year
Assessment Tools	
Ankle Brachial Index
 
HbA1c
 
Monofilament test for neuropathy
 
Photograph
 
E-Z Graph Wound Assessment System
 
Sf-36v2 Health Survey

Primary Endpoint	Proportion of subjects who have a closed wound at or before 12 weeks after the index procedure.
Primary Hypothesis	
As an observational study, there is no formal hypothesis test. The precision of the estimate of the proportion of subjects who successfully close will be determined.
 
Assumptions:
 
 • A minimum 50 subjects • A 95% Confidence Interval of the estimate • A 2-sided confidence interval • Using exact Clopper-Pearson estimation 
The Confidence Intervals (CI) at selected success rates are as follows:
 
 • @ 25%; CI = 25.4% Boundaries 13.8%-39.3% • @ 50%; CI = 28.9% Boundaries 35.5%-64.5% • @ 75%; CI = 25.4% Boundaries 60.7%-86.2% 
Thus, a sample size of 50 should allow for a reasonable estimate of treatment success at 12 weeks and for reasonable comparisons to historical controls.

Statistical Analysis	
Descriptive statistics including but not limited to mean, standard deviation, frequency and percentages will be used to describe demographics, medical history, and characterize baseline variable as appropriate.
 
A Z-test will be used to assess whether the proportion of subjects that were successful is greater than zero. Kaplan-Meier analysis will be used describe the survival curve assuming complete closure as the event of interest. A repeated measure ANOVA will be used to assess changes in, wound area and quality of life over time.

TABLE OF CONTENTS

1	Background	13

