1 BACKGROUND

More than 23 million people (7.8%) in the United States are believed to have diabetes. Annually, 1 to 4 percent of people with diabetes develop a foot ulcer and that 10 to 25 percent of diabetic patients will have at least one foot ulcer during their lifetime (1) (2).

Diabetic foot ulcers (DFUs) are a chronic wound which commonly result from peripheral neuropathy and/or peripheral arterial disease associated with diabetes (3). The economic impact of DFUs as a subset of chronic wounds is considerable. An estimated annual \$25 billion is spent on treatment of chronic wounds, and diabetes-related amputations cost approximately three billion dollars per year (2). In addition to treatment-related costs, disability and lost wages related to chronic wounds represents a heavy socioeconomic burden (2).

Standard care for treating DFUs address multiple issues and can vary between care providers. Common standard care considerations include wound debridement, pressure reducing strategies, restoring blood flow, maintaining a moist wound environment, wound infection management, and nutritional support (4). Supplemental treatment for chronic ulcers can include topical antimicrobials, hyperbaric oxygen treatment, cellular therapy, growth factors, and skin substitutes. Accelerated healing of chronic DFUs with skin substitutes can improve patient outcomes and mitigate the economic impact of DFUs.

MIRODERM® is a biologic, porcine liver derived, acellular wound treatment matrix. MIRODERM is FDA 510(k) cleared with an indication for the management of wounds including diabetic ulcers (K140510 and K143426). In addition to being porcine based, MIRODERM has several novel properties including an outer facing epithelial basement membrane with a wound facing open collagen matrix and an intact highly vascularized structure. Both of these are thought to improve the probability of epithelialization and cellular integration. Initial data suggest that MIRODERM can be effective in closing long open DFUs which have been refractory to standard of care and other biological products (5)

This clinical trial will rigorously document the ability of MIRODERM to treat hard-to-heal DFUs and further characterize the safety profile of this device.

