3 RATIONALE

As a novel, highly vascular porcine derived biologic it is believed that MIRODERM wound biologic may heal wounds more successfully and in a shorter time. The rationale is to objectively demonstrate the clinical effectiveness of MIRODERM by empirically determining the proportion of wounds closed and fully describe the time course to closure.

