6.5.10 Off-Loading Device fitting and instruction

Subject will be fitted with an off-loading device and given instruction on use.

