6.10.3 Demographics, Medical Conditions and Medical Co-morbidities CRF

This will document subject's demographics including but not limited to, date of birth, gender, height, weight, BMI, ethnicity, current tobacco use and current alcohol use.

Current medical conditions and parameters, especially relative to inclusion and exclusion criteria, will be documented. This may include but is not limited to, HbA1c level, Ankle-Brachial Test, transcutaneous oxygen pressure test, (TcPO₂), toe pressure test, and Monofilament Test.

History and current conditions of the DFU will be documented including but not limited to duration of ulcer, maximum height, length and depth, number of previous attempts to close with a biological solution and biological wound treatments previously used.

The subject's medical co-morbidities and history will document major system concomitant pathologies, drug allergies and current medication use.

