6.10.11 Transcutaneous Oxygen Pressure Test (TcPO2)

A TcPO2 test is a non-invasive test to quantify skin oxygenation and is indicative of cutaneous ischemia. TcPO2 levels above 30 mmHg are predictive for spontaneous healing while values of 10 mmHg or less are predictive of an unfavorable course of healing. To be used as the inclusion criteria for this study, potential subjects should, within 90 days of Assessment and Roll-In, have a documented TcPO2 value equal or greater than 30 mmHg.

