Thus, a sample size of 50 should allow for a reasonable estimate of treatment success at 12 weeks and for reasonable comparisons both to the literature and a history of not healing.

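### A non-healing history (an implied 0% closure rate) is not a usable comparator in this single-arm study, and testing closure against zero does not show a device effect

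*Combined protocol and SAP*

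**What the plan says.** Section 7 first gives exact 95% intervals for 50 subjects. It then concludes that this number is enough "for reasonable comparisons both to the literature and a history of not healing". The matching sentence in the synopsis (Primary Hypothesis) is worded differently: "for reasonable comparisons to historical controls". Neither place gives a benchmark rate or a source for one.

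The synopsis (Statistical Analysis) adds a test: "A Z-test will be used to assess whether the proportion of subjects that were successful is greater than zero". Section 3 states the purpose: "The rationale is to objectively demonstrate the clinical effectiveness of MIRODERM by empirically determining the proportion of wounds closed". Both the synopsis and Section 7 also say that there is no formal hypothesis.

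On care before the study, Section 6.5.2 requires an ulcer of at least 90 days' duration that stayed open after at least two biologic treatments. It requires no particular prior off-loading or debridement. Section 1 notes: "Standard care for treating DFUs address multiple issues and can vary between care providers".

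On care within the study, the roll-in visit (Sections 6.5.7 to 6.5.11) provides sharp debridement as necessary, a specified moist dressing changed daily by the subject, nutrition instruction and off-loading: "Subject will be fitted with an off-loading device and given instruction on use". MIRODERM follows two weeks later, with weekly visits from then on (Section 6.1). An ulcer found closed at the treatment visit gets no MIRODERM (Section 6.6.1), and subjects count as enrolled only once treated.

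**The concern.** Comparing closures on study with each subject's own non-healing past treats the expected closure rate without the device as 0%. The period before and the period after differ in more than MIRODERM. Care before entry is uncontrolled, whereas care from roll-in onward is largely set by the protocol. A closure could come from the device, from the rest of the package or from the ulcer's natural course, and one arm cannot tell these apart.

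The 0% is also produced by the entry rule. An ulcer that had closed would not be eligible, so the past closure rate among subjects is zero by construction, whatever their chance of closing over the next 12 weeks.

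At stake is the effectiveness statement. Any reasonable number of closures will look like success against zero, and Section 3 invites the reader to credit it to the device.

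**Working it through.** **1. The plan's own figures.** Inputs from Section 7: n = 50, two-sided 95%, Clopper-Pearson. The lower limit is the 0.025 quantile of Beta(x, n − x + 1), and the upper limit is the 0.975 quantile of Beta(x + 1, n − x).

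- x = 12.5 (25%): 13.84% to 39.26%, width 25.4 points
- x = 25 (50%): 35.53% to 64.47%, width 28.9 points
- x = 37.5 (75%): 60.74% to 86.16%, width 25.4 points

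All three agree with the plan. (The 25% and 75% rows use non-integer counts, which does not matter here.) The calculation concerns precision only. It says nothing about what the proportion may be compared with.

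**2. What it takes to beat zero.** A Z-test that uses the null variance is undefined here, since 0 × (1 − 0)/50 = 0. I therefore assume the unpooled (Wald) form, z = p / √(p(1 − p)/n), at the 0.05 level. The synopsis gives neither the form nor the sidedness.

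- 3/50: 0.06 / √(0.06 × 0.94 / 50) = 0.06 / 0.0336 = 1.79, significant one-sided (1.645) but not two-sided (1.96)
- 4/50: 0.08 / √(0.08 × 0.92 / 50) = 0.08 / 0.0384 = 2.09, significant two-sided

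**3. How often that happens with no device effect.** Let b be the 12-week closure rate under the study's other care. The documents give no value, so b is an assumption, shown from 5% to 30%. The third column is P(X ≥ 4) for X ~ Binomial(50, b). The last is the smallest count whose exact lower 95% limit exceeds b.

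| Assumed b | Expected closures (50 × b) | P(at least 4 of 50) | Closures needed for lower limit above b |
|---|---|---|---|
| 5% | 2.5 | 24% | 7 |
| 10% | 5 | 75% | 10 |
| 15% | 7.5 | 95% | 14 |
| 20% | 10 | 99% | 17 |
| 30% | 15 | about 100% | 23 |

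Four closures beat zero, but against a 20% background 17 would be needed.

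**4. Does roll-in remove the problem?** Three provisions bear on this.

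- Section 6.6.1 diverts an ulcer only if it is closed at the treatment visit.
- Section 6.10.17 measures size for inclusion at the roll-in visit, after debridement. No later size or area-change requirement exists.
- The same section has the wound traced again at the treatment visit.

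Take an ulcer that shrinks substantially over the two weeks but is not closed. It receives MIRODERM, is enrolled, and counts as a success if it closes by week 12. Roll-in therefore removes the fastest responders to the other care and keeps the rest. The two tracings that would show who was responding are already collected, but no analysis of them is specified.

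**The case against.** The strongest defence is that the study calls itself observational and states no formal hypothesis, that the history phrase is a closing remark about precision, and that the literature is named as a second comparator. Roll-in is also a real safeguard: the other care starts before the device, and ulcers that close on it alone are not enrolled. This stands as far as it goes. It does not remove the Z-test from the synopsis or the effectiveness claim from Section 3, and two weeks without an area-change criterion is only a partial screen.

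Four stronger readings are tempting, and the documents do not support them.

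- **That off-loading, debridement and nutrition instruction start together with MIRODERM.** They start at roll-in, two weeks earlier. Only the weekly visits begin with the first application.
- **That the study admits ulcers it regards as likely to heal by themselves.** Section 6.10.11 does say "TcPO2 levels above 30 mmHg are predictive for spontaneous healing", but that describes a measurement level. TcPO2 is one of three alternative perfusion routes, and every ulcer must also have lasted 90 days and stayed open after two biologic treatments.
- **That the care was new to subjects.** Section 1 lists debridement, pressure reduction, a moist wound environment and nutritional support among common standard care, so some subjects may already have had all of it. What the documents show is that prior care is not controlled.
- **That prior-care data are missing for good.** Section 6.10.3 names "number of previous attempts to close with a biological solution and biological wound treatments previously used" and not prior off-loading or debridement, but its list is expressly open. The sample forms in Appendix B are not in the supplied text, and Sections 8 and 9 give the sponsor access to source records.

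It is also fair to say that an exact interval lying above 0% does not measure the confounding. A single closure in 50 already has a lower limit of 0.05%. That shows only how little a zero reference can tell.

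**Conclusion.** The concern holds in this form: the comparison with a non-healing history, and the test against zero that goes with it, cannot support attributing closures to MIRODERM. Uncontrolled prior care, protocol-driven care from roll-in, selection on past failure and the absence of a concurrent control all enter the same difference.

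The size of the confounding is unknown, because the documents give no closure rate for this care without the device. What can be shown is how weak the zero reference is: with no device effect, a background of 10% to 20% would pass the two-sided test about 75% to 99% of the time. At 5% the figure is 24%. These figures assume n = 50, independent subjects and a Wald test at 0.05.

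The closure proportion and its exact interval remain valid as a description of subjects treated under this protocol. The sample-size arithmetic is correct and need not change.

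**What to change.** 1. In the last sentence of Section 7, keep the literature and delete the reference to the subjects' history. Delete the Z-test from the synopsis. Report the closure proportion with its exact Clopper-Pearson interval.
2. State in Sections 3, 4.1 and 7 that this proportion describes MIRODERM given with debridement, off-loading, nutrition instruction and weekly care, and that it is not attributed to the device by comparison with the subject's own past.
3. Report percent area change from Visit 1 to Visit 2, and show 12-week closure by that change. Both tracings are already taken.
4. Optionally, record from the chart whether off-loading and sharp debridement were in use in the 90 days before Visit 1. Treat this as descriptive context only: it would not separate the device from the rest of the package.
5. Limit literature comparisons to cohorts in which off-loading and debridement were part of care, and align the synopsis wording on historical controls with this.

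The cost is wording in the synopsis and three sections, one descriptive table and, if chosen, two chart items. No visit, procedure or sample size changes. The downsides are a narrower effectiveness statement and wide subgroup intervals: 12 closures in a subgroup of 25 would give 27.8% to 68.7%, a width of 40.9 points, against 28.9 points for 25 of 50 overall.
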